4.3. ATIMP Administration

ATIMP administration volume and study eye data will be summarized by study phase and dose and listed.

4.4. Protocol Deviations

Subjects with major protocol deviations will be identified prior to database lock. Subjects with major protocol deviations will be summarized and an accompanying listing will be provided.

Delayed and missing visits due to COVID-19 will be tabulated and listed.

4.5. Prior and Concomitant Medications

Prior and concomitant medications will be coded using the World Health Organization Drug Dictionary (WHO-DD). Prior medications are defined as any therapy initiated before the day of ATIMP administration. Concomitant medications are defined as any therapy used on or after the day of ATIMP administration, including those that started before and continue on or after ATIMP administration.

Summaries of prior and concomitant medications by Anatomical Therapeutic Chemical (ATC) term will be presented by treatment group, age group and overall. The proportion of subjects who receive each medication will be summarized as well as the proportion of subjects who receive at least 1 medication.

Concomitant medications of interest (e.g., medication for management of inflammation/corticosteroids) will also be presented.

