1.3. Statistical Hypotheses for Trial Objectives

1.3.1. Primary Safety Hypothesis

The objective of the dose escalation phase is to estimate the proportion of subjects who experienced the primary safety outcome. No formal hypothesis testing will be conducted.

The primary safety outcome is defined as any of the events delineated below and occurring during the 9 weeks following administration, at least possibly related to the ATIMP, not the surgery alone:

- Reduction in visual acuity by 15 Early Treatment Diabetic Retinopathy Study (ETDRS) letters or more
- Severe unresponsive inflammation (defined in Section 4.2.1 of the protocol)
- Infective endophthalmitis
- Ocular malignancy
- Grade III or above non-ocular suspected unexpected serious adverse reaction (SUSAR) (Protocol MGT009, Section 5.11.3.4.2 Severity or Grading of Adverse Events).

Safety will be assessed for 12 months following ATIMP administration for immediate treatment participants in this study (Protocol MGT009) by study phases (dose escalation, dose confirmation and expansion phases) and overall, comparing with 6 months data in deferred treatment arm prior to treatment. Safety outcome captured in a separate long-term follow-up study (Protocol MGT010) for a further 4 years will be summarized separately.

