2.5. Study Day and Relative Day

Study Day 1 refers to the day of ATIMP administration for subjects in the dose escalation phase and dose confirmation phase, as well as immediate treatment subjects in dose expansion phase. For deferred treatment subjects during the deferred period prior to treatment, Study Day 1 refers to the end date of the last baseline visit. For deferred treatment subjects during the post-treatment

period, Study Day 1 refers to the day of ATIMP administration. All efficacy and safety assessments at all visits will be assigned a day relative to this date.

Study day (or relative day) for a visit is defined as:

- Visit date - (date of Study Day 1) +1 day, if the visit date is on or after Study Day 1
- Visit date - date of Study Day 1, if the visit date is before Study Day 1

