2.7. Imputation Rules for Missing AE Date and Resolution

Partial adverse event (AE) onset dates will be imputed as follows:

- If the onset date of an AE is only missing the day, it will be imputed as:
 - First day of the month that the AE occurred, if month/year of the onset of the AE is different than the month/year of ATIMP administration
 - The day of ATIMP administration, if the month/year of the onset of AE is the same as month/year of ATIMP administration and month/year of the AE resolution date is different
 - The day of ATIMP administration or day of AE resolution date, whichever is earliest, if month/year of the onset of AE and month/year of ATIMP administration and month/year of the AE resolution date are same
- If the onset date of an AE is missing both day and month, it will be imputed to the earliest of:
 - January 1 of the year of onset, as long as this date is on or after ATIMP administration
 - Month and day of ATIMP administration, if this date is the same year that the AE occurred
 - Last day of the year if the year of the AE onset is prior to the year of ATIMP administration,
 - The AE resolution date.
- Completely missing onset dates will not be imputed.

Partial AE resolution dates not marked as ongoing will be imputed as follows:

- If the resolution date of an AE is missing day only, it will be set to the earliest of the last day of the month of occurrence of resolution or the day of the date of death, if the death occurred in that month.

- If the resolution date of an AE is missing both day and month, it will be set to the earliest of December 31 of the year or the day and month of the date of death, if the death occurred in that year.

Completely missing resolution dates will not be imputed.

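### SAP 4.5 classes medication by the ATIMP day only, so therapy confined to the deferred arm's control period is tabulated only as prior medication

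*SAP*

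**What the plan says.** SAP 4.5 gives two definitions, both keyed to one date. The first is "Prior medications are defined as any therapy initiated before the day of ATIMP administration". The second is "Concomitant medications are defined as any therapy used on or after the day of ATIMP administration, including those that started before and continue" to or beyond that day. On display it says "Summaries of prior and concomitant medications by Anatomical Therapeutic Chemical (ATC) term will be presented by treatment group, age group and overall", and it adds a presentation of medications of interest, with corticosteroids as an example. It names no other date and has no separate rule for the deferred arm before treatment.

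SAP 2.5 treats that arm differently: "For deferred treatment subjects during the deferred period prior to treatment, Study Day 1 refers to the end date of the last baseline visit". The ATIMP day becomes Study Day 1 only for its post-treatment period. SAP 1.3.1 plans to report safety in the immediate arms "comparing with 6 months data in deferred treatment arm prior to treatment", and SAP section 6 gives the primary safety outcome for deferred subjects before treatment as well as for immediate subjects. Under SAP 2.3.3 a deferred participant enters the safety set on completing the last baseline assessment, so dosing is not required.

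SAP 2.7 also uses the ATIMP date as its only anchor for partial AE onset dates. With the day missing, the imputed onset is "First day of the month that the AE occurred, if month/year of the onset of the AE is different than the month/year of ATIMP administration". In the ATIMP month it is the ATIMP day, or the resolution date if that is earlier in the same month. With day and month missing, the earliest of several candidates is taken. One is "Month and day of ATIMP administration, if this date is the same year that the AE occurred"; another is the resolution date.

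**The concern.** The deferred arm before treatment is the trial's concurrent control. For a safety comparison, a reader wants to see which drugs, steroids above all, controls used while under observation. That question has an answer only if medication use is classified relative to the start of the control period. SAP 4.5 classifies it relative to an event that happens when the control period ends.

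The consequence is a table that does not match the SAP's own period structure. A drug taken in month 4 of follow-up is concomitant in an immediate-arm participant. In a control, if stopped before ATIMP, it is prior, in the same class as a drug stopped years before consent. Programmers must either follow the text and produce columns that are not like for like, or choose a rule of their own.

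The single anchor in SAP 2.7 raises a related but smaller question: whether partly dated AEs from the control period are kept in it.

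**Working it through.** **Medication classes.** No arithmetic applies, so I set the rules of SAP 4.5 against the periods of SAP 2.5 for a deferred participant.

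| Therapy | Prior | Concomitant |
|---|---|---|
| Stopped before control Day 1 | yes | no |
| Started before control Day 1, stopped during control | yes | no |
| Started and stopped during control | yes | no |
| Started during control, continues to or past ATIMP | yes | yes |
| Started on or after ATIMP | no | yes |
| Any therapy, participant never dosed | undefined | undefined |

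The first three rows receive the same label, although only the first lies wholly outside control follow-up. The fourth row does reach the concomitant table, but as use after treatment. No cell isolates use during the control period. The last row can occur: Protocol 5.4.9.1 allows for withdrawal before administration, and SAP 2.3.3 can still count such a person in the safety set.

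The period concerned is 6 months by plan, for up to 16 participants. SAP 1.2 reports delays beyond that, and the visit windows in SAP 2.1 run to Day 365. The data exist: Protocol 5.4.7 requires medications to be recorded from the day of consent.

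**Partial AE dates.** The plan states no figure here. The rules of SAP 2.7 were applied to every onset day in a control period, with control Day 1 set to each of 730 consecutive calendar dates from 1 January 2019. Assumptions not in the documents: onset is uniform over the period; the AE lasts 7 days, lasts 30 days, or has no resolution date. Control length was 183 days (the Week 26 target day) or 365 days (the window limit).

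| Missing | Length | Moved to ATIMP day (7 d / 30 d / no resolution date) | Set before control Day 1 | Stays |
|---|---|---|---|---|
| Day | 183 | 3.3% / 8.1% / 8.1% | 8.1% | 83.9% to 88.6% |
| Day | 365 | 1.7% / 4.0% / 4.0% | 4.0% | 91.9% to 94.3% |
| Day and month | 183 | 3.8% / 15.7% / 74.8% | 0.0% | 25.2% to 96.2% |
| Day and month | 365 | 1.9% / 7.9% / 49.9% | 0.0% | 50.1% to 98.1% |

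Two hand checks:

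- Day missing. If control Day 1 is day d of an n-day month (d of 2 or more), the n − d + 1 control days left in that month are all dated to the 1st, before Day 1. Averaged over d this is (n − 1)/2. With n = 365/12 = 30.4 that is 14.7 days: 14.7/183 = 8.0% and 14.7/365 = 4.0%. The ATIMP month gives the same average, because d − 1 control days precede ATIMP.
- Year only, no resolution date. For control length L, the share of control days in the ATIMP year averages 1 − L/(2 × 365): 1 − 183/730 = 74.9% and 1 − 365/730 = 50.0%.

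Three kinds of record therefore leave the control period: day-missing onsets in the month of control Day 1; day-missing onsets in the ATIMP month not resolved earlier in that month; and year-only onsets in the ATIMP year with no earlier resolution date.

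**The case against.** Anchoring medication on first investigational product is a common and coherent convention, and for a deferred participant the label is literally true. Control-period drugs are not lost: they are in the prior table, and those that continue past ATIMP are counted as concomitant too. The tables are descriptive, and no test, estimand or imputation uses the classes. All of that stands, and it is why this is a minor point. It does not answer the gap: the SAP makes the control period a safety comparator but provides no view of medication use during it.

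On AE dates the objection is stronger. Most day-missing control AEs stay where they belong. Where a partial date fits either period, assigning it to ATIMP is conservative for the product. A day-missing AE in the month of control Day 1 may truly precede Day 1, since AEs are recorded from consent (Protocol 5.11.3.5.1). Scheduled AE review and data queries should make year-only dates rare.

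Three stronger readings are tempting, and the documents do not support them:

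- A reader might infer that the date rule distorts the immediate-versus-deferred safety comparison. The AE tables of SAP 6.1 count only events on or after ATIMP, so control-period AEs fall outside them however they are dated. The primary safety outcome in SAP 1.3.1 requires an event after administration.
- A reader might infer that the concomitant table holds nothing started in the control period. Therapy continuing to or past ATIMP is there.
- A reader might try to quantify how far the deferred arm's prior column is inflated. The documents give no rate of new drug use, *prior* has no lower time limit, and the start of observation differs between arms (randomisation, baseline visits, COVID-19 extensions). Any percentage would be an assumption.

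**Conclusion.** The medication point holds on the text alone. SAP 4.5 uses one anchor where SAP 2.5 defines two, so therapy confined to the control period appears only as prior, the by-arm concomitant and corticosteroid displays have no control-period column, and a never-dosed deferred participant has no class. It concerns up to 16 controls. How many medication records are affected cannot be known from the documents. Efficacy and the primary safety outcome are untouched.

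The AE-date point holds only in a narrow form: some partly dated deferred-arm AEs shift out of the control period, mainly at its two boundary months. The shares above rest on uniform onset and the assumed durations, and apply only to partly dated records, whose number is unknown and probably small. The large year-only shares need a missing month and no resolution date together. The shift would matter only in a tabulation of control-period AEs, which SAP 6.1 as written does not produce.

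**What to change.** In SAP 4.5, replace the ATIMP day by Study Day 1 of the relevant period as defined in SAP 2.5. Nothing changes for the dose-escalation, paediatric and immediate-treatment participants, whose Study Day 1 is the ATIMP day. For the deferred arm, report three classes, allowing a therapy to appear in more than one:

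1. started before control Study Day 1;
2. used from control Study Day 1 to the day before ATIMP. This is the control column. Flag separately the oral steroid prophylaxis that Protocol 5.4.1.6 places in the week before ATIMP, so that it is not read as background steroid use;
3. used on or after ATIMP.

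For a deferred participant never dosed, class 2 runs to the end of follow-up and class 3 is empty. Use the same split for the corticosteroid display.

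In SAP 2.7, for any table of control-period AEs, impute a missing day in the month of control Study Day 1 to that day, or to the resolution date if earlier in that month, mirroring the ATIMP rule. A new anchor cannot settle an AE whose partial date fits both periods, so show such AEs on a period-unknown line.

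The cost is SAP wording and derivation code. Medications and AEs are already recorded from consent, so no new data are needed.

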4.6. Medical History and Ophthalmic History

Medical history findings will be summarized using Medical Dictionary for Regulatory Activities (MedDRA) by Primary System Organ Class/High Level Term.

Ophthalmic history apart from the study condition will be summarized and an accompanying listing will be provided.

4.7. Genetic Testing

A listing of genetic testing data on nucleotide and protein sequence based on screening for RPGR mutations prior to enrollment will be provided.

5. EFFICACY

Unless otherwise specified, efficacy analyses will be based on the efficacy analysis set and statistical tests will be interpreted at a two-sided significance level of 0.05, with confidence intervals presented at a 2-sided level of 95%.

5.1. Changes to the Protocol

This SAP will not define slowing or halting of progressive deterioration using baseline variation, as defined in Protocol v12.0. Instead, this SAP will assess the visual function endpoint readout in immediate treatment group compared with deferred treatment group.

5.2. Changes to the SAP

The original SAP (dated 24 May 2019) described analyses of the test-retest variation for each visual function assessment, however, this will not be assessed given that the assessments of efficacy endpoints focus on the effect of the treated eye in immediate treatment group compared to the deferred participant treatment eye in deferred group. The statistics for the test-retest do not fit the purposes of the stated objectives and are not appropriate for the goals of the study.

5.2.1. Data Handling Rules

In the case where a variable is recorded as “ $>x$ ”, “ $\geq x$ ”, “ $<x$ ” or “ $\leq x$ ”, for analysis purposes a value of x will be taken. Where a range of values is quoted the midpoint of the range will be taken. For example, if a laboratory safety parameter is reported as being below the limit of quantification or $<x$, the value of the limit will be used in the calculation of summary statistics. The recorded value will be reported in listings. As sensitivity analysis, for endpoints from static perimetry assessment, including pointwise responder, mean retinal sensitivity, central 30 degree hill of vision (V30), assessment with reliability factor greater than 19% is deemed not reliable and will be excluded according to MeiraGTx Working Practice on Octopus 900 Static perimetry.

For safety, there will be no imputation for missing values for physical examination results, ocular examination, vital sign measurements, clinical laboratory test results and other safety endpoints in the analyses.

5.3. Primary Efficacy Endpoint

5.3.1. Definition

The primary efficacy endpoint is evaluated in subjects from the dose expansion phase based on point-by-point data from 185-point static perimetry assessed through Week 26 in the randomized immediate treatment subjects and compared with randomized deferred subjects in the 26-week deferred period (prior to treatment). Subjects will be considered a responder if they experience at least 7 dB improvement from baseline at 5 or more loci at Week 13 and Week 26; this determination will be based on the treated eye for subjects in the immediate treatment group and for the deferred participant treatment eye for subjects in the deferred group, who had static perimetry assessments at both Week 13 and Week 26. Subjects with missing visits in either Week 13 or Week 26 will not be counted as responder or non-responder and will not contribute to number of subjects in the denominator when calculating proportion of responders.

Treated eye refers to a treated eye in a participant who was assigned or randomized to immediate treatment in any period of the study. Randomized concurrent control eye refers to an untreated eye in a participant who was randomized to deferred treatment; these eyes will receive treatment after completion of the 6-month deferral period. For the purposes of the primary efficacy analyses, these eyes represent the randomized concurrent control group.

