5.6.1 Early Stopping of Follow-up

If a participant chooses to discontinue their trial treatment, they should continue to be followed up as closely as possible to the follow-up schedule defined in the protocol, providing they are willing. If, however, the participant exercises the view that they no longer wish to be followed up either, this view must be respected. Data already collected will be kept and included in analyses according to the intention-to-treat principle for all participants who stop follow up early.

Participants who stop trial follow-up early may be replaced.

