The study conduct was substantially impacted by the COVID-19 pandemic. In particular, the pandemic caused delayed and missed visits to several subjects in the randomized dose expansion phase of the study. In addition, there were delays beyond the planned 6 months for treatment in the deferred treatment arm of the study. To allow greater flexibility in the management of protocol

deviations and timing of treatments in the deferred treatment arm of the study as a result of the COVID-19 pandemic, the protocol was amended in accordance with Health Authority guidance.

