5.3.2. Estimand

The primary estimand, the main clinical quantity of interest to be estimated in the study, is defined by the following components:

- Population: subjects of age 5 years or above with *RPGR-XLRP*
- Treatment: subretinal administration of AAV5-hRKp.RPGR at low and intermediate doses (pooled) for immediate treatment arm and 6-month deferred treatment for deferred treatment arm
- Variable: retinal sensitivity response defined by point-by-point data from 185-point static perimetry
- Intercurrent event: none
- Strategy for addressing intercurrent events: treatment policy strategy
- Population-level summary: Difference in the proportion of responders in retinal sensitivity between immediate treatment subjects and deferred treatment subjects and associated 95% confidence interval

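### The primary responder analysis drops anyone missing Week 13 or Week 26, including subjects already known to be non-responders, and has no missing-data sensitivity analysis

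*SAP*

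**What the plan says.** SAP 5.3.1 defines a responder as a subject with "at least 7 dB improvement from baseline at 5 or more loci at Week 13 and Week 26" in the relevant eye. It then sets the missing-data rule: "Subjects with missing visits in either Week 13 or Week 26 will not be counted as responder or non-responder", and such subjects "will not contribute to number of subjects in the denominator when calculating proportion of responders". SAP 5.3.3 repeats the rule for the stratified Fisher test.

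Other parts of the plan describe a wider group:

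- SAP 5.3.2 gives the estimand as "Population: subjects of age 5 years or above with" RPGR-XLRP, with no condition on visits attended. It also lists "Intercurrent event: none" and "Strategy for addressing intercurrent events: treatment policy strategy".
- SAP 2.3.2 admits an expansion-phase subject to the Full Analysis Set (FAS) with a baseline and one later visit. Immediate subjects must have been treated, and deferred subjects need a visit before treatment. Analysis follows the assigned arm.
- Protocol 5.6.1, on participants who stop follow-up early, says: "Data already collected will be kept and included in analyses according to the intention-to-treat principle".
- SAP 1.2 reports that "the pandemic caused delayed and missed visits to several subjects in the randomized dose expansion phase of the study". No counts are given.
- SAP 5.5 puts the primary endpoint first in the testing sequence, so no secondary endpoint is formally tested unless it succeeds.

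**The concern.** The rule makes the primary test a complete-case analysis, in a subset defined by attendance after randomisation. Comparability between the arms then depends on why visits were missed, and the plan neither states an assumption about this nor tests one.

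The rule also discards outcomes that are already settled. Because both visits must meet the criterion, one observed failure is enough to classify a subject. The SAP treats him as unclassifiable all the same.

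With at most 32 immediate and 16 deferred subjects, a handful of missed visits could decide the primary result and, through the gate, whether any secondary endpoint is tested.

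**Working it through.** **1. Inputs.** From the documents: 1:1:1 allocation with up to 16 per arm, so pooled immediate up to 16 + 16 = 32 against deferred up to 16 (Protocol 5.9.1); two-sided alpha 0.05 (SAP 5); Fisher's exact test stratified by age under 25 or 25 and over (SAP 5.3.3). The protocol states that there is no formal sample size calculation, so there is no planned response rate, missing rate or power to reproduce. All responder and missing counts below are assumptions. The tests are unstratified because stratum sizes are not given.

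**2. Visit patterns against the responder definition.**

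| Week 13 | Week 26 | Status by the definition | SAP rule |
|---|---|---|---|
| meets | meets | responder | counted |
| both attended, fails at least one | | non-responder | counted |
| fails | missing | non-responder, settled | dropped |
| missing | fails | non-responder, settled | dropped |
| meets | missing | undetermined | dropped |
| missing | meets | undetermined | dropped |
| missing | missing | undetermined | dropped |

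Every dropped subject is either a settled non-responder or undetermined. No confirmed responder can be dropped.

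**3. How many of the dropped are settled.** If a proportion q of subjects meet the criterion at Week 13, and missing Week 26 is unrelated to that result, the settled share of those missing only Week 26 is 1 − q. For assumed q of 0.43 to 0.50 this is 0.57 to 0.50, so about half or slightly more.

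**4. Effect on one arm's rate.** With true response rate p and missing probabilities m_R in responders and m_N in non-responders, the complete-case rate tends to p(1 − m_R) / [p(1 − m_R) + (1 − p)(1 − m_N)].

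- p = 0.30, m_R = 0, m_N = 0.20: 0.30 / (0.30 + 0.70 × 0.80) = 0.30 / 0.86 = 34.9%.
- p = 0.30, m_R = m_N = 0.10: the rate stays at 30%.
- p = 0.30, m_R = 0.20, m_N = 0.05: 0.24 / (0.24 + 0.665) = 26.5%.

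The rate can be overstated, unchanged or understated, depending on the reason for missingness. The same applies in each arm, so the difference between arms can move either way.

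**5. Effect on the p-value (two-sided Fisher exact).** Every missing subject is counted as a non-responder in the comparison column.

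| Assumed responders | Assumed missing | SAP rule | Missing as non-response |
|---|---|---|---|
| 7 vs 0 | 4 immediate, 0 deferred | 7/28 vs 0/16, p = 0.037 | 7/32 vs 0/16, p = 0.079 |
| 8 vs 0 | 0 immediate, 3 deferred | 8/32 vs 0/13, p = 0.083 | 8/32 vs 0/16, p = 0.039 |
| 7 vs 0 | 7 immediate, 2 deferred | 7/25 vs 0/14, p = 0.036 | 7/32 vs 0/16, p = 0.079 |
| 7 vs 0 | 7 immediate, 3 deferred | 7/25 vs 0/13, p = 0.072 | 7/32 vs 0/16, p = 0.079 |
| 8 vs 0 | 7 immediate, 2 deferred | 8/25 vs 0/14, p = 0.034 | 8/32 vs 0/16, p = 0.039 |

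Row 1 favours the treatment and row 2 goes against it. Rows 3 to 5 show how fragile a crossing is: one more missing deferred subject, or one more responder, removes it.

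**6. Search for a safeguard.** The stated sensitivity analyses pool phases (SAP 1.3.2 and 2.2), add natural-history data (2.2), or exclude unreliable fields (5.2.1), which removes more data. SAP 5.4.2 allows model-based imputation for efficacy where appropriate. That sentence is unspecific, sits under the secondary endpoints, and does not override the explicit primary rule.

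**The case against.** A reader might infer that the rule contradicts the treatment policy strategy. The documents do not support this. That strategy governs intercurrent events, SAP 5.3.2 names none, and a missed visit is missing data. The mismatch is between the analysed subset and the estimand population. Naming a strategy with no event to apply it to is a separate gap.

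A reader might also infer a general breach of intention-to-treat. Protocol 5.6.1 speaks only of participants who stop follow-up early. It reaches someone who gave Week 13 data and then left, but not an isolated visit missed because of COVID-19. The SAP also cites protocol v12.0, while the supplied amendment log ends at v11.0, so the wording in force could not be checked. Nor is the SAP's efficacy set all randomised subjects: it is the FAS.

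Missingness may be small. The windows in SAP 2.1 are wide (immediate Week 13 is Day 73 to 160 and Week 26 is Day 161 to 259; deferred Week 26 runs to Day 365), and late deferred visits count as Week 26. These absorb delays but cannot supply a visit that never took place.

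Finally, one might argue that surgery causes missed fields in the treated arm only. No section says so. Protocol 5.11.3.4.4 describes the expected acuity loss as temporary, up to 8 weeks, and the Week 13 window opens at Day 73.

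These points limit the claim. They do not explain why a subject with an observed failure is called unclassifiable.

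**Conclusion.** The point holds as a defect in the handling of missing data. The rule conditions the primary analysis on attendance after randomisation, discards settled non-responders, and sets aside Week 13 data from early stoppers that the supplied protocol says are kept and analysed. No stated sensitivity analysis tests it. The classification argument follows from the responder definition alone and needs no assumption about why visits are missed.

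It would go too far to say that the rule inflates the treatment effect. Missing counts by arm and reasons for missing are not given, so neither the size nor the direction of bias in the comparison can be derived. The p-values show only that, at up to 32 versus 16, three or four exclusions can be enough to cross 0.05 in either direction. They rest on chosen counts and an unstratified test, and many nearby counts show no crossing.

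**What to change.** Amend SAP 5.3.1 and 5.3.3 for the expansion-phase FAS:

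1. Classify anyone who fails the criterion at an observed Week 13 or Week 26 visit as a non-responder and keep him in the denominator.
2. For subjects still undetermined, pre-specify one primary method, for example multiple imputation by arm and age stratum.
3. Report non-responder imputation, the complete-case result and a tipping-point analysis as sensitivity analyses, with missing counts and reasons by arm.
4. Align the estimand text in 5.3.2 with the chosen handling.

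Steps 1 and 2 belong together. Counting observed failures while still dropping undetermined subjects would pull the rate down even if visits were missed purely at random.

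The cost is SAP wording and a little more analysis work. The reported responder proportions may be slightly lower.
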